### Carriage and Anthropometric cohorts

Since outcomes are actively recorded in these cohorts, missing data may be recorded for some of the outcomes analysed in the Carriage and Anthropometric cohorts.

We anticipate some missing data at the 4-month time point because of the interruption due to the COVID-19 pandemic. Therefore, an available case analysis will be conducted in the Carriage cohort. The occurrence of missing data is unlikely to be associated with any particular characteristic of the women/neonates, and the risk of bias due to missing data is small.

The anthropometric cohort was recruited prior to the COVID-19 pandemic. Nevertheless, we expect some missing data due to loss to follow up, and will therefore conduct an available case analysis in this cohort. We will assess the risk of selection bias by comparing the baseline characteristics of children who are lost to follow up with those who remain in the cohort throughout follow up.

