## Baseline covariates

To avoid having to exclude individuals because of missing covariate data, we will impute missing values of birthweight and 1-minute Apgar score with mean values. In the Carriage cohort, imputation will be unnecessary because having baseline carriage data is an inclusion criteria for this cohort.

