### **Infant carriage**

With the exception of *Klebsiella*, which is tested for in NPS and RS, in samples collected from infants each bacteria is only tested for in one sample type (e.g. *S. pneumoniae* is tested for in NPS and *E.coli* is tested for in rectal swabs). Therefore, in contrast to the analysis of maternal carriage, there is no need to combine results across different sample types. Each bacteria will be compared between study arms at day 0, day 6, day 28 and 4 months (Table 4). Additionally, we will compare the proportion positive at any time point. We will use logistic regression to adjust for maternal carriage at day 0 if the prevalence is  $\geq 4\%$ , if the prevalence is less than this then we will calculate an unadjusted OR and use Fisher's exact test. Note that we have chosen to adjust for maternal carriage at day 0 rather than neonatal carriage because neonatal samples are collected after treatment and may, therefore, be affected by treatment. The prevalence at each time point and in each arm will be displayed graphically. As with the analysis of maternal carriage, the analyses will be

done in children with complete data and then repeated using multiply imputed data (missing day 28 and 4-month outcomes will be imputed from day 0 and day 6 outcomes).

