### 8.3 Anthropometric cohort

Standardised anthropometric Z-scores (WHZ, WAZ, HAZ and MUAC-for-age, head-circumference-for-age) based on WHO 2006 growth charts will be calculated using the Stata package “zanthro” (Vidmar et al., 2013).

As recommended in the WHO report on data quality in anthropometric studies

<https://www.who.int/nutrition/publications/anthropometry-data-quality-report-chapter3.pdf>, a flag system will be used to recode implausible z-score values as missing:

- height-for-age:  $< -6$  or  $> +6$
- weight-for-length/height:  $< -5$  or  $> +5$
- weight-for-age:  $< -6$  or  $> +5$

- body mass index-for-age:  $< -5$  or  $> +5$

For each anthropometric measure, we will compare between study arms the mean score at 6 months, 12 months, and growth velocity, i.e. difference between 6 and 12-month scores. Linear regression will be used to calculate a difference between arms and p-value adjusted for country, birth weight and 1-minute Apgar score. The continuous variables (birth weight and Apgar score) will be included in the model as linear terms.

In addition, we will dichotomise the Z-scores using  $< -2$  SD as the cut-off for malnutrition and  $< -3$  SD as the cut-off for severe malnutrition. We will use logistic regression to adjust for country, birth weight and 1-minute Apgar score.

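### Separate available-case regressions at 6 and 12 months leave the 6-month scores of children lost later out of the 12-month and change contrasts, and the planned drop-out check specifies no look at 6-month growth or at arm

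*SAP*

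**What the plan says.** Section 6.4 (Carriage and Anthropometric cohorts) anticipates losses in the growth cohort: "we expect some missing data due to loss to follow up, and will therefore conduct an available case analysis in this cohort". Its one safeguard is to assess selection bias by "comparing the baseline characteristics of children who are lost to follow up with those who remain in the cohort throughout follow up". It names neither study arm nor 6-month growth, and no further analysis follows if a difference is found.

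Section 8.3 sets three contrasts for each measure: "the mean score at 6 months, 12 months, and growth velocity, i.e. difference between 6 and 12-month scores". The model is fixed: "Linear regression will be used to calculate a difference between arms and p-value adjusted for country, birth weight and 1-minute Apgar score". For the dichotomised scores: "We will use logistic regression to adjust for country, birth weight and 1-minute Apgar score". No repeated-measures term is planned, and the 6-month score is not a covariate at 12 months.

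Imputation for this cohort is limited to covariates (section 6.4, Baseline covariates): "we will impute missing values of birthweight and 1-minute Apgar score with mean values". Section 8.2 does more for carriage. The complete-data analyses are repeated on multiply imputed data, and for infants "missing day 28 and 4-month outcomes will be imputed from day 0 and day 6 outcomes".

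**The concern.** The 6-month z-score is probably the best available predictor of a missing 12-month z-score, and the 12-month and change analyses do not use it for children lost in between. This has two possible consequences.

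- **Precision.** Information already collected is left out of two of the three contrasts.
- **Bias.** If poorly growing children leave after 6 months at different rates in the two arms, the arm losing more of them looks better at 12 months. A comparison restricted to baseline characteristics is not designed to detect loss related to growth after birth, and without a split by arm it does not address the pattern that distorts an arm comparison.

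The SAP is also uneven. Section 6.4 considers missing carriage data unlikely to be related to participant characteristics, yet carriage gets multiple imputation. For growth it raises selection bias as a risk and plans no model-based analysis of it.

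**Working it through.** **Inputs.** The SAP gives no power, drop-out, SD or correlation figure for growth, so there is no stated result to reproduce. Assumed:
- SD of the z-score 1.2 at both visits, and no true arm difference
- 6-to-12-month correlation r = 0.7 (0.6 to 0.8 for precision)
- mean z-score μ of 0, -0.5 or -1
- low growth means a 6-month z-score below -1; 10% of all other children are lost after 6 months
- 5 to 20% of 12-month scores missing, for precision

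**Precision.** With all children seen at 6 months and a fraction m missing at 12 months (unrelated to growth), the standard error of the 12-month mean using the 6-month scores, relative to available cases, is √(1 − r²m).

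| m | r = 0.6 | r = 0.8 |
|---|---|---|
| 0.05 | 0.991 | 0.984 |
| 0.10 | 0.982 | 0.967 |
| 0.20 | 0.963 | 0.934 |

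The standard error falls by about 1 to 7%. The planned models already contain birth weight, so the relevant partial correlation is probably lower and the gain smaller.

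**Bias.** Let p be the loss among low-growth children in an arm, c = (−1 − μ)/1.2, and φ and Φ the standard normal density and distribution function. The proportion retained is 0.9 − (p − 0.1)Φ(c). The available-case 12-month mean is shifted upwards by

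0.7 × 1.2 × φ(c) × (p − 0.1) / [0.9 − (p − 0.1)Φ(c)].

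The false arm difference is the shift in one arm minus the shift in the other. Example for μ = -0.5: c = -0.417, φ = 0.3658, Φ = 0.3385.
- p = 0.30: 0.84 × 0.3658 × 0.20 / 0.8323 = 0.0738
- p = 0.15: 0.84 × 0.3658 × 0.05 / 0.8831 = 0.0174
- difference: 0.056

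| μ | 15% v 15% or 30% v 30% | 20% v 15% | 30% v 15% | total loss by arm at 30% v 15% |
|---|---|---|---|---|
| 0 | 0 | 0.014 | 0.042 | 14.0% v 11.0% |
| -0.5 | 0 | 0.018 | 0.056 | 16.8% v 11.7% |
| -1 | 0 | 0.020 | 0.065 | 20.0% v 12.5% |

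Simulation of the same rule gave 0.014 to 0.021 and 0.042 to 0.066, which agrees within simulation error. An estimate that also uses the 6-month scores gave 0.000 to 0.001 at 30% v 15%. The change contrast is biased the other way by a factor (1 − 0.7)/0.7, which gives -0.018 to -0.028 at 30% v 15%.

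**Scale.** The unadjusted 95% half-width, 1.96 × 1.2 × √(1/n₁ + 1/n₂), after the losses at 30% v 15%, is 0.112 to 0.115 with 1,000 per arm at entry. With 500 per arm it is 0.159 to 0.163. Both sizes are needed because the endpoint heading in section 3.4 gives 1,000 infants, whereas sections 4.1 and 4.4 give 2,000.
- 30% v 15%: the bias is about 37 to 56% of the half-width (1,000 per arm) or 26 to 40% (500 per arm).
- 20% v 15%: about 12 to 18%, or 9 to 13%.

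**Cross-check.** A second simulation used a true difference of 0.10 SD at both visits and r = 0.6 or 0.8, adjusted for birth weight.
- Loss unrelated to growth, or related equally in both arms: available cases gave 0.09 to 0.105.
- Loss depending on the 6-month score in one arm only: 0.11 to 0.13 at 5% loss, 0.12 to 0.16 at 10%, and 0.145 to 0.21 at 20%. Total losses were nearly equal by arm (for example 21% v 20%).
- Using the 6-month scores: 0.093 to 0.106 throughout.

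**The case against.** Separate adjusted regressions at two visits are a conventional, fully specified analysis of secondary endpoints in a sub-cohort. The trial is double-blind with a single dose in labour, and nothing in the SAP suggests that poorly growing infants would leave at different rates by arm 6 to 12 months later. The 30% v 15% scenario is severe, and its imbalance in total loss would normally be visible in a participant flow diagram. The proposed model also rests on an untestable assumption. All of this stands, and it keeps the point small.

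Four stronger readings are tempting, and the document does not support them.
- *The 6-month scores of children lost later are discarded.* They enter the 6-month comparison. They are missing only from the 12-month and change contrasts.
- *The drop-out check is pooled over arms.* Section 6.4 is silent on arm. No comparison by arm is specified, which is different from a decision to pool.
- *Selective loss goes uncorrected.* Adjustment for country, birth weight and Apgar score handles loss explained by those variables.
- *The 12-month comparison is valid only if loss is unrelated to 6-month growth.* The calculation shows no bias in the arm difference when growth-related loss is the same in both arms.

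What the objection does not remove is that a better method is already in use elsewhere in the same SAP. Equal loss counts would also not exclude the problem, as the cross-check shows.

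**Conclusion.** The point holds as a minor one. The planned 12-month and change analyses leave out relevant 6-month data, and the planned check would not be expected to reveal growth-related loss that differs by arm. On assumed inputs, the cost is a 12-month standard error about 1 to 7% larger than necessary. The possible false 12-month difference runs from nil (loss equally related to growth in both arms) through 0.014 to 0.020 z (20% v 15% low-growth loss) to 0.042 to 0.065 z (30% v 15%). None of these rates comes from the SAP, so they show what could happen, not what is expected. The primary endpoint is unaffected.

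**What to change.** Replace the separate linear regressions in section 8.3 by one repeated-measures model for each continuous z-score. It should have visits at 6 and 12 months, arm by visit, visit-specific effects of country, birth weight and Apgar score, and an unstructured covariance. Take all three contrasts from it. Alternatively, multiply impute 12-month scores from 6-month scores, in line with section 8.2. Imputation has the advantage that the dichotomised outcomes can be derived from the same imputed scores.

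In section 6.4, add a table by arm of loss after 6 months and of the 6-month z-scores of children later lost, with deaths shown separately. Reconcile the cohort size between section 3.4 and sections 4.1 and 4.4.

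Cost: SAP wording and a little more programming in the Stata or R already named, with no new data. Limit: both methods assume that scores are missing at random given the 6-month score and the covariates, so neither corrects loss driven by unobserved growth after 6 months.

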## Baseline covariates

To avoid having to exclude individuals because of missing covariate data, we will impute missing values of birthweight and 1-minute Apgar score with mean values. In the Carriage cohort, imputation will be unnecessary because having baseline carriage data is an inclusion criteria for this cohort.

## 6.5 Interim Analyses and Data Monitoring

Data on baseline characteristics, incidence of primary outcome, numbers recruited, numbers under follow up, have been presented at DSMB meetings.

No further interim analyses are planned.

## 6.6 Accounting for differences between countries

(ICH E3; 9.7.1, 11.4.2.4. ICH E9; 3.2)

The regression models used to analyse outcomes in the Primary and Anthropometric cohorts will include country. Hence these analyses will be adjusted for country (in addition to 1-minute Apgar score and birthweight). In the analysis of the Primary cohort, we will do separate analyses in each country using a Wald test to test the treatment x country interaction. This analysis will be considered to be exploratory. No adjustment for country will be made in the analysis of the Carriage cohort because of the smaller size of this cohort.

## 7 Summary of Study Data

See dummy tables and consort diagram.

## 8 Efficacy Analyses

### 8.1 Primary analysis cohort

#### Primary outcome

We will report the proportion that meet the criteria for the primary outcome (death or sepsis within 28 days of birth) in each arm.

The null hypothesis of no difference between the arms will be tested by fitting a logistic regression model that, in addition to study arm, includes 1-minute Apgar score and birthweight as continuous, linear covariates. The p-value, odds ratio and

confidence interval associated with study arm will be reported, with the confidence interval and p-value being based on a Wald test.

### **Mortality and sepsis**

Mortality and sepsis will be analysed separately, as secondary outcomes, as well as being part of the primary outcome.

They will be analysed as binary outcomes and as time to event outcomes using Kaplan Meier curves. In the K-M analysis of sepsis, death will be treated as a censoring event. There will be no censoring in the analysis of mortality because any neonate whose day 28 survival status is unknown is excluded from the Primary cohort.

A concern in the analysis of composite endpoints is that of competing risks. In this analysis, death is a competing risk for sepsis – an individual who has died is not at risk of sepsis. Although some bias due to the competing risk of death is expected in the K-M analysis of sepsis, the bias will be small because death is a rare outcome.

### **Secondary outcomes**

The secondary outcomes are all binary and will therefore be analysed using logistic regression as described for the primary outcome (except the specific aetiologies of sepsis which will be analysed using Fisher's exact test because these are rare outcomes).

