### **Subgroups**

Exploratory analyses in which the data are stratified by country will be done for all outcomes analysed in the Primary cohort. In addition, the primary outcome will be analysed in the following subgroups:

- Deliveries >2 hours after administration of the study pills
- Deliveries  $\leq 2$  hours after administration of the study pills
- Deliveries in the wet season (June–October)
- Deliveries in the dry season (November–May)
- Overweight and obese mothers ( $BMI \geq 25.0 \text{ kg/m}^2$ )
- Normal weight and underweight mothers ( $BMI < 25.0 \text{ kg/m}^2$ )
- Newborns delivered via caesarean
- Vaginal deliveries

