### **Covariate adjustment**

Where possible, regression models will be used to improve statistical power (Kahan, 2014). We will use linear regression for continuous outcomes and logistic regression for binary outcomes.

In the analysis of outcomes in the Primary and Anthropometric cohorts, the models will include country as a binary predictor, and 1-minute Apgar score and birthweight as continuous linear terms.

In the analysis of data from the Carriage cohort, logistic regression will be used to adjust for day 0 maternal carriage (day 0 neonatal carriage cannot be adjusted for because it is recorded after treatment).

No covariate adjustment will be used in the analysis of the aetiologies of sepsis (Primary cohort) because the prevalence of the outcomes in this analysis is anticipated to be low and logistic regression may be unreliable in this situation (Peduzzi et al., 1996).

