## **8.2 Carriage cohort**

### **Maternal carriage**

Maternal bacterial carriage will be analysed by estimating the proportion of women positive at day 6 and the proportion positive at one or more of the post-intervention time points (i.e. day 6, day 28 or 4 months). The latter will be estimated using women who have data available at all time points, i.e. women missing day 28 or 4-month data will be excluded from this analysis. However, a secondary analysis will be done using a multiply imputed dataset in which missing day 28 and 4-month carriage data are imputed using day 0 and day 6 data. For bacteria that are isolated from multiple sample types an individual will be identified as positive if bacteria are isolated from any of the samples (Table 5). For example,

women will be considered positive for *Klebsiella* at day 6 if bacteria are isolated from either the NPS or breast milk sample. Besides presenting the prevalence of individual bacteria, the bacteria will be grouped into gram positives (*S. pneumoniae*, *S. aureus*, GBS, GAS) and gram negatives (*E. coli*, *pseudomonas*, *Klebsiella*).

We will use logistic regression to compare the proportion positive by study arm adjusting for carriage at day 0. For example, *S. aureus* carriage on day 6 will be compared by calculating an odds ratio adjusted for *S. aureus* carriage on day 0. If the prevalence of a carriage outcome is <4% then an unadjusted odds ratio will be presented instead of the adjusted OR and Fisher's exact test will be used to calculate the p-value. The cut-off of 4% has been chosen to ensure that logistic regression is not used when there are fewer than 10 events per parameter as recommended by Peduzzi et al (1996).

A longitudinal analysis of carriage will be conducted using data from breast milk samples collected on day 6, day 28 and at 4 months. As with the other analyses, logistic regression will be used to adjust for carriage at day 0 where possible (i.e. provided the prevalence is  $\geq 4\%$ ). Two versions of the analysis will be done: the first will be restricted to women with complete data at all three time points, and the second will be done using the multiply imputed dataset. The prevalence at each time point and in each arm will be displayed graphically.

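### Secondary outcomes in the Primary cohort have no sparse-event rule beyond sepsis aetiologies, so the rarest ones, chiefly post-partum mortality, may lack a usable odds ratio and Wald interval (minor)

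*SAP*

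**What the plan says.** **Model.** Section 8.1 (Secondary outcomes) reads: "The secondary outcomes are all binary and will therefore be analysed using logistic regression as described for the primary outcome". The only exception is the specific aetiologies of sepsis, which go to Fisher's exact test. The primary-outcome model reports an odds ratio "with the confidence interval and p-value being based on a Wald test".

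**Covariates.** Section 8.1 lists three terms: arm, Apgar score and birthweight. Section 6.3 (Covariate adjustment) has four, because "the models will include country as a binary predictor, and 1-minute Apgar score and birthweight as continuous linear terms"; section 6.6 confirms country.

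**By country.** Section 6.3 (Subgroups) adds: "Exploratory analyses in which the data are stratified by country will be done for all outcomes analysed in the Primary cohort". Section 6.6 adds a Wald test of treatment by country and says: "This analysis will be considered to be exploratory".

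**Rare outcomes elsewhere.** Section 6.3 drops adjustment for sepsis aetiologies because their prevalence is "anticipated to be low and logistic regression may be unreliable in this situation". In section 8.2 (Maternal carriage) a 4% cut-off is set so that "logistic regression is not used when there are fewer than 10 events per parameter". Infant carriage follows the same rule: "if the prevalence is less than this then we will calculate an unadjusted OR", with Fisher's test.

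**Safety.** Section 9 counts hospitalisations and deaths in mothers and neonates of the Primary cohort and tests them by Fisher's exact test.

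**The concern.** The SAP recognises the sparse-data problem and has a rule for it, but applies the rule only to carriage outcomes and sepsis aetiologies. Section 3.4 lists other Primary-cohort outcomes that may be as sparse: post-partum mortality above all, and possibly culture-confirmed sepsis and deaths among VLBW newborns. For these, section 8.1 prescribes the adjusted Wald model at any event count.

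If one arm has no events, the maximum-likelihood odds ratio is not finite, the Wald standard error is meaningless and the interval says nothing. The estimator would then have to be chosen after the data are seen. In the country analyses, where counts are smaller, this is more likely.

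**Working it through.** **1. The SAP's own cut-off.** Carriage cohort 500 (section 4.1): 0.04 × 500 = 20 events; two terms (arm, day 0 carriage); 20 / 2 = 10 events per parameter. The 4% reproduces exactly.

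**2. The same standard in the Primary cohort.**
- Four terms (section 6.3): 4 × 10 = 40 events, or 40 / 12,000 = 0.33%.
- Three terms (section 8.1, or any model within one country): 3 × 10 = 30 events, or 30 / 12,000 = 0.25% when pooled.

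**3. Outcomes with a rate in the SAP.** Rates are from section 5; numbers recruited (6,750 and 5,250) are from section 4.1.
- Sepsis, The Gambia: 0.019 × 6,750 = 128.25. Burkina Faso: 0.018 × 5,250 = 94.5. Pooled: 222.75. All clear the threshold.
- Mortality at 0.7%: 0.007 × 12,000 = 84 pooled; 47.25 and 36.75 by country. These clear it only if the 0.7% already leaves out the causes that the endpoint excludes (severe asphyxia, VLBW, major malformation). If it counts all deaths, the endpoint falls below the threshold once the excluded share exceeds 1 − 30/36.75 = 18% in Burkina Faso, 1 − 30/47.25 = 37% in The Gambia, or 1 − 40/84 = 52% pooled. The SAP does not settle which applies.

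**4. Outcomes without a rate: break-even shares.**
- Culture-confirmed sepsis reaches 40 pooled only if at least 40/222.75 = 18% of sepsis cases are culture-positive. For 30 within a country the shares are 30/128.25 = 23% (The Gambia) and 30/94.5 = 32% (Burkina Faso).
- VLBW deaths, if 0.7% counts all deaths, reach 40 pooled only if 40/84 = 48% of deaths are in VLBW newborns. For 30 within a country the shares are 64% and 82%. If 0.7% already excludes VLBW deaths, no bound follows.

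**5. Post-partum mortality: assumed range.** Take average rates r of 0.05, 0.10 and 0.15%, which give 6, 12 and 18 deaths in 12,000. That is 1.5, 3 and 4.5 events per parameter with four terms, or 2, 4 and 6 with three. All are below 10.

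With n per arm and no treatment effect, P(at least one arm empty) = 2(1 − r)^n − (1 − r)^(2n). Example: r = 0.0005, n = 6,000 gives (0.9995)^6000 = 0.0497, and 2 × 0.0497 − 0.0497² = 0.097.

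| | n per arm | 0.05% | 0.10% | 0.15% |
|---|---|---|---|---|
| Overall | 6,000 | 9.7% | 0.5% | 0.02% |
| The Gambia | 3,375 | 34% | 6.7% | 1.3% |
| Burkina Faso | 2,625 | 47% | 14% | 3.9% |

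**6. What an empty arm does.** For 0 versus 6 deaths in 6,000 per arm, a fitted logistic model gave a log odds ratio near −20, a standard error in the thousands and Wald p above 0.99. Fisher's p is 0.031 and the exact 97.5% upper limit for the odds ratio is 0.85. For 0 versus 4 deaths the upper limit is 1.51. The exact method gives a usable limit where the planned one gives none.

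**7. Cost of switching.** Rejection rates, unadjusted Wald versus Fisher, 6,000 per arm, risk ratio 0.7:

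| Events | Wald | Fisher |
|---|---|---|
| 12 | 5.5% | 5.1% |
| 18 | 9.6% | 7.6% |
| 24 | 12.5% | 9.6% |
| 36 | 17.4% | 14.6% |

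**The case against.** **Maternal death already has a valid test.** A reader might infer that the SAP leaves maternal death without any workable analysis. It does not: section 9 pre-specifies counts and Fisher's exact test for deaths in mothers of the Primary cohort. This objection stands. Only the effect estimate and its interval are left open.

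**The wording is softer than a mandate.** Section 6.3 introduces regression as something to be used where possible, and says only that logistic regression may be unreliable at low prevalence. That is fair, but the phrase sets no threshold and names no alternative. The carriage cut-off of 4% cannot be carried over either: it would remove the primary outcome itself, expected at 2.0 to 2.8% by arm in Table 6.

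**The fallback costs something between the empty-arm case and 40 events.** This stands. Unadjusted Wald stays below 5% rejection under no effect at 12 to 36 events and rejects more often than Fisher when there is an effect. The narrower rule, confined to empty arms, would cure the worst failure.

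**Two p-values for one endpoint.** Neonatal hospitalisation, maternal hospitalisation and maternal death are tested in both section 8.1 and section 9. A reader might see a multiplicity problem or frequent contradiction. The documents do not support that. The section titles already separate efficacy from safety. At the assumed maternal mortality, an empty arm together with Fisher p < 0.05 occurs in at most about 1.4% of trials, for risk ratios of 1 and 0.7, overall or within a country. This is a matter of wording, as is the choice of newborn covariates for mothers of twins.

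**Conclusion.** The point holds and is minor. Section 8.1 states a rule that, followed literally, can fail for the sparsest secondary outcomes, and it departs from the standard the SAP sets for carriage. Post-partum mortality is the likeliest case; culture-confirmed sepsis and VLBW mortality are possible ones. The neonatal-death endpoint may also fall short, within Burkina Faso first, if the 0.7% counts all deaths.

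The empty-arm figures rest on an assumed maternal mortality of 0.05 to 0.15%, equal arms, no treatment effect and no loss from the numbers recruited. Above roughly 12 deaths a pooled empty arm is improbable; the estimate then exists but falls short of 10 events per parameter. Most of the risk lies in the country analyses, which are exploratory. A reader might extend the concern to the primary outcome, but at the expected incidence it is far above the threshold: sepsis alone contributes about 223 events.

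**What to change.** In section 8.1 (Secondary outcomes), extend the SAP's own fallback, overall and by country, as an event count and not a percentage:

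- When events are fewer than 10 per model parameter, report counts by arm, an unadjusted odds ratio with exact confidence interval, and Fisher's exact p-value. Use non-events where these are the smaller number, as may happen for VLBW mortality.
- State the threshold for the model actually used: 40 with the four terms of section 6.3; 30 with the three terms of section 8.1 or within a country.
- At the least, apply this whenever an arm has no events, and do not compute the section 6.6 treatment-by-country Wald test when a cell is empty.

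Two clarifications can go in at the same time: that the section 8.1 result is the efficacy result where section 9 repeats the test, and which newborn's Apgar score and birthweight are used for a mother of twins.

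The cost is a few sentences and no new data. Outcomes under the threshold lose covariate adjustment, and Fisher rejects somewhat less often than unadjusted Wald (step 7 of the working). The gain is a usable interval and a method fixed in advance, not power. The primary-outcome model needs no change on this account.
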